Methods: PIONEER will be a three-arm, programmatic cluster randomized controlled trial (RCT) to compare the effectiveness of the three implementation strategies, followed by a mixed-methods implementation evaluation study guided by a transformative paradigm. For the cluster RCT, we will enroll 12 diverse clinics, which will be randomly assigned to one of the intervention arms for delivering gonorrhea testing: a standard pay-it-forward implementation strategy with minimal encouragement to get tested, a community-engaged pay-it-forward strategy, and a control arm in which men pay for their own STD test. The public and MSM-led clinics in the same city will be randomized to the same study group to prevent contamination. The primary outcome of the RCT will be gonorrhea test uptake, and secondary outcomes will include chlamydia testing, STD treatment among those with infection, amount donated, 100% condom use, and antimicrobial resistance. A sequential explanatory mixed methods design will be used to evaluate the implementation process. Data sources will include survey data on the acceptability of the intervention, intervention appropriateness, feelings and attitudes towards the interventions among participants, administrative data about test uptake, treatment rate, and donations, as well as qualitative data to gain insights about men's perceptions and attitudes towards the pay-it-forward interventions strategies, mechanisms driving uptake and donating behaviors. Both survey and qualitative interviews with implementers and organizers about fidelity and adherence to protocol, intention to continue and maintain a pay-it-forward intervention, and barriers and facilitators of implementing the intervention will be conducted.

Discussion: PIONEER will substantially increase gonorrhea testing among MSM in China, providing an innovative new financial mechanism to sustain STD screening among sexual minorities in low- and middle-income countries. This study will answer compelling scientific questions about how best to implement pay-it-forward and the individual and organizational characteristics that moderate it.

Contributions to the literature

- This cluster randomized controlled trial aims to examine the effectiveness of two implementation strategies involving different levels of community engagement to translate the generosity created by the pay-it-forward approach into test-taking action.

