Mixed methods will be used to evaluate the implementation process with project implementers, organizers, and participants. Data sources will be multiple, which will include survey data on the acceptability of the intervention, intervention appropriateness, feelings and attitudes towards interventions among participants, administrative data about test uptake, treatment rate, and donations, as well as qualitative data to gain insights about men's perceptions and attitudes towards the pay-it-forward interventions strategies, mechanisms driving uptake and donating behaviors. Both survey and qualitative interviews with implementers and organizers about fidelity and adherence to protocol, intention to continue and maintain a pay-it-forward intervention, and barriers and facilitators of implementing the intervention will be conducted.

Study setting and population

We will implement the study in Guangdong cities with either (or both) public STD and MSM-led clinics. Examples include Zhuhai, Foshan, Jiangmen, Zhanjiang, Zhanjiang, Dongguan, and Huizhou. These clinics were chosen because respective cities have a higher burden of STDs, and findings would be potentially relevant in many cities. In MSM-led clinic, only MSM who

meet eligibility criteria will be included. In public STI clinics, all men will be recruited. The rationale for this is that many MSM do not identify as being attracted to other men.

The study settings between public clinics and MSM-led clinics would be different. One key obstacle to recruiting MSM at public STD clinics is that MSM usually may not want to disclose their sexual identities due to justifiable fears about risks of stigma and discrimination from other men and health workers. Therefore, to avoid indirect sexual orientation disclosure and feelings of discrimination, public STD clinic recruitment will be extended to include all men visiting the public clinic setting regardless of sexual orientation. This will lower the risk of being unnecessarily 'targeted' and accidental sexual orientation disclosure.

The inclusion criteria at public clinics include men who are at least 18 years old; have had sex over the past year; have not been tested for gonorrhea and chlamydia in the past year; reside in the city in the past three months; speak Mandarin Chinese or Cantonese; mentally capable of providing informed consent to test for gonorrhea and chlamydia; and owning a mobile phone.

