A co-creation group will be appointed and will comprise MSM representatives, clinicians and nurses, communication officers, and co-chaired by members of SESH and a local MSM community-based organization. Co-creation groups serve as a source of shared leadership in CBPR-premised research, and its members typically reflect the community of interest. This co-creation group will be consulted on a quarterly basis to provide input on the study design, implementation, and dissemination activities.

Site selection, training, and trial registration

We will implement the study in Guangdong cities with MSM-led clinics: Huizhou, Zhuhai, Jiangmen, Foshan, Zhanjiang, and Dongguan. These clinics were chosen because respective cities have a higher burden of STDs, they include the two major service delivery approaches (MSM-led clinics and public clinics) in China, and findings would be potentially relevant in many cities that have chlamydia/gonorrhea point-of-care testing available.

Each of the clinical sites will receive Good Clinical Practice (GCP) training for new personnel, regulatory assessment, and related trial requirements. Representatives from each of the participating clinics will be invited to attend a single training workshop in Guangzhou to introduce the study protocol, local implementation workflows, sample collection and testing, gonorrhea and chlamydia treatment, and the resistance testing processes. We registered the RCT on ClinicalTrials.gov (registration id: NCT05723263) prior to the commencement of the trial.

Developing standard strategy and the community-engaged strategy

This three-arm cluster randomized controlled trial will compare gonorrhea test uptake in a standard pay-it-forward implementation strategy arm, a community-engaged pay-it-forward implementation strategy arm, and a control arm. Our implementation strategies are summarized in Table 1.

Table 1. Overview of the three study arms.

Trial Arm	Financial Component of Gonorrhea Testing*	Community Engagement
Standard Pay-it-forward arm	Free gonorrhea/ chlamydia testing	Passive: viewing postcards and materials written by others encouraging gonorrhea/ chlamydia testing Active: an opportunity

		to donate to support others.

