We have developed an interview guide as part of formative testing. The main topics in the interview guide will include the following: (1) reasons for getting tested; (2) understanding and perception of the pay-it-forward concept; (3) specific questions about emotions of gratitude after receiving a test that is supported by another community member; and (4) self-identity in the MSM community and level of integration within a community; (5) intention and motivation to initiating and mediating helping behaviors within the community. We will obtain recorded verbal informed consent from all interviewees before the commencement of the interview. Interviews will last about one hour and will take place either in person or over the phone-based on participant preference.

Interviews will be audio-recorded, and personal information will not be recorded. Unintentional recording of personal information will otherwise be redacted before transcription. Each participant will receive a small monetary incentive of ¥50 (7.50 USD) for their participation. All recorded interviews will be transcribed, and the transcripts will be checked by one research staff member. Summaries of interviews will be written up for preliminary data analysis. In addition, we will collect anonymized text from handwritten postcards and other community engagement activities.

Pragmatic cluster RCT

Sample size and power considerations

We used a binary outcome cluster RCT design for sample size calculation where the unit of randomization is the clinic. In order to achieve a 90% power and allow for 0.05 type-I error, 12 overall clusters (4 in each arm) are needed. Thus, the sample size includes a total of 12 clusters and 1200 participants (100 per cluster) based on cluster randomized trial sample size calculation principles. We expect this study will have 85% power to detect a 10% difference in azithromycin resistance between intervention arms and routine gonorrhea antibiotic surveillance data from other cities in the same province. Nevertheless, further calculations will be made following formative research endeavors that will estimate the prevalence of these outcomes. The calculation would be performed using the software PASS (version 15) with the formulas developed by Hussey and colleagues.³⁶

Randomization

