Figure 2 shows the cluster RCT design flowchart. We will assign clinics to study arms on a 1:1:1 basis using covariate-constrained randomization. We will use covariate-constrained randomization to decrease potential bias associated with unbalanced study arms. We will balance the number of MSM-led and public clinics in each arm because these are unique implementation structures. All men recruited via one clinic will be assigned to one arm. We will recruit and screen men until we meet our sample size of 1200 men.

[figure not shown]

Figure 2. Pragmatic RCT flowchart. Each city will have one MSM-led clinic and one public clinic participating.

Intervention delivery strategies

The duration of the intervention is one year at each clinic, with the potential to continue based on local commitments. All patients who accept testing will receive gonorrhea/chlamydia PCR testing. This diagnostic is approved by the US FDA and the Chinese national regulatory authority. Men who agree to be tested will have specimens collected from

pharyngeal, rectal, and urethral sites. Specimens will be pooled based on excellent sensitivity and specificity. Turnaround time for test results will depend on the local clinic. Surveys will be done online in order to facilitate implementation. All participants diagnosed with gonorrhea will receive ceftriaxone and azithromycin in accordance with WHO recommendations for first-line gonorrhea therapy.

Outcome measures

The primary outcome of the RCT will be gonorrhea test uptake ascertained by administrative review from participating clinics. We used this same primary outcome in previous quasi-experimental and RCT trials evaluating pay-it-forward. Secondary outcomes will include syphilis testing, amount donated towards pay-it-forward, antimicrobial resistance measures, positive tests for gonorrhea and chlamydia, measures of gratitude and community solidarity, and per unit costs associated with the intervention (Table 2).

Table 2. Secondary outcomes of the cluster RCT			
Outcome	Time Frame	Ascertainment	Data Analysis
Primary			
Gonorrhoea and Chlamydia test uptake		Clinic administrative data	Generalized mixed effects models (compare control arm to pay-it-forward intervention)
Secondary			
Amount donated	During enrollment visit	Administrative data	Descriptive analysis
The number of participants who tested positive for Gonorrhea	During enrollment visit	Laboratory result	Descriptive analysis

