The number of participants tested positive for chlamydia	During enrollment visit	Laboratory result	Descriptive analysis
The proportion of those who tested positive for Gonorrhea or Chlamydia who returned for referral treatment	One month after receiving the results	Self-reported follow-up survey (linkage to care, treatment)	Descriptive analysis
Cost per test ¹	During enrollment visit	Costing data collection	Micro-costing approach

Adapted gratitude scale	During enrollment visit	Self-report	T-test
Community solidarity scale ⁴	During enrollment visit	Self-report ²	T-test
Community cohesion	During enrollment visit	Self-report	T-test
Internalized homophobia	During enrollment visit	Self-report	T-test
Subgroup analysis			
Gonorrhea and chlamydia testing uptake by clinic type	During enrollment visit	Administrative data at study site	MSM-led clinic vs. public STD clinic
Gonorrhea and chlamydia testing uptake by sexual orientation	During enrollment visit	Self-reported sexual orientation data from baseline survey	Self-identified sexual minority vs. not
Gonorrhea and chlamydia testing uptake by age group	During enrollment visit	Self-reported socio-demographic data from baseline survey	≤30years vs. >30years
Gonorrhea and chlamydia testing uptake by PrEP eligibility	During enrollment visit	Self-reported frequency of condom use in during sexual intercourse in the past 3 months data from baseline survey	Condom use vs. Condomless sex.

¹Cost per test is defined as the cost associated with respective interventions (development, start-up, implementation, intervention) per individual who reported testing for gonorrhea and chlamydia following the intervention; economic test and financial cost are reported separately.
 
²Community solidarity involves engagement, social network support, and a sense of belonging. These items were used in our previous pay-it-forward research study..
			

Data analysis

Data will be analyzed using a transformative mixed method research approach. The primary outcome will be gonorrhea and chlamydia test uptake among MSM. Quantitative and qualitative data will be analyzed using a convergent parallel design (i.e., analyze quantitative

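### Table 2 names only a t-test for four self-reported scales in a cluster-randomized trial, with no allowance for clustering and no arm pairs

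*Combined protocol and SAP*

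**What the plan says.** Table 2 lists four scales that each man reports at enrolment. The first and last rows read "Adapted gratitude scale During enrollment visit Self-report T-test" and "Internalized homophobia During enrollment visit Self-report T-test"; the rows for community solidarity and community cohesion name the same test. No row says which two of the three arms are compared, or how men from one clinic are handled.

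On allocation, the sample size section of the cluster RCT says "the unit of randomization is the clinic", with 12 clinics, 4 per arm, and 100 men in each. The abstract (Methods) adds: "The public and MSM-led clinics in the same city will be randomized to the same study group to prevent contamination". The Randomization section says "We will balance the number of MSM-led and public clinics in each arm because these are unique implementation structures", and the Design overview says that randomization also takes the economic status of the city into account. The Figure 2 caption states "Each city will have one MSM-led clinic and one public clinic participating".

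Mixed models appear in three places: the primary-outcome row of Table 2, the two main hypotheses in the RCT Data analysis section, and the correlates of implementation scores in the Data analysis section of the implementation evaluation. None of these covers the between-arm comparison of the four scales.

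**The concern.** A two-sample t-test on individual men treats 400 men per arm as 400 independent observations. Here an arm is represented by four clinics or, if cities are the allocated unit, by two cities. Men who attend the same clinic, or live in the same city, may resemble each other in gratitude or sense of community for reasons unrelated to the arm. The test then understates the standard error, so p-values are too small and intervals too narrow.

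At stake are four listed secondary outcomes. Gratitude and community solidarity bear on the second objective, which asks how pay-it-forward motivates testing and donating. A chance difference between a few clinics or cities could be reported as a mechanism.

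**Working it through.** **The plan's own figure.** The stated 90% power concerns the binary primary outcome. No uptake rates, effect size or ICC are given, so it cannot be reproduced. No power is stated for the scales, and nothing below depends on that figure.

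**Inputs from the documents.** 100 men per clinic; 4 clinics and 400 men per arm; both clinics of a city in one arm, hence 2 cities per arm and 200 men per city if there are six cities with two clinics each.

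**Assumed.** The ICC remaining after the balanced factors; any difference between clinic types (d, in SD); any difference between city economic strata; a two-sided 5% level.

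**Step 1: t-test on individual men, no effect of the balanced factors.** Design effect DE = 1 + (m − 1) × ICC. True error = 2 × [1 − Φ(1.96/√DE)]. For example, m = 100 and ICC 0.01 give DE = 1 + 99 × 0.01 = 1.99, 1.96/√1.99 = 1.39, error 16.5%.

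| ICC | DE, clinic (m = 100) | Error | DE, all at city level (m = 200) | Error |
|---|---|---|---|---|
| 0.001 | 1.099 | 6.2% | 1.199 | 7.4% |
| 0.005 | 1.495 | 10.9% | 1.995 | 16.5% |
| 0.01 | 1.99 | 16.5% | 2.99 | 25.7% |
| 0.02 | 2.98 | 25.6% | 4.98 | 38.0% |
| 0.05 | 5.95 | 42.2% | 10.95 | 55.4% |

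With only 50 or 25 respondents per clinic and a clinic ICC of 0.01, DE is 1.49 or 1.24 and the error 10.8% or 7.8%.

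**Step 2: effect of clinic type.** Type is balanced, so a difference between types adds to the variance that the t-test uses but not to the variance of the arm difference. DE is replaced by DE/(1 + d²/4). With no residual ICC the error is 5.0% / 4.3% / 2.8% for d = 0 / 0.5 / 1. The test becomes liberal once 99 × ICC exceeds d²/4, that is, above ICC 0 / 0.0006 / 0.0025. At ICC 0.01 the error is 16.5% / 15.2% / 12.0%.

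**Step 3: t-test on unadjusted clinic means (6 df).** With d = 0.5 and ICC 0.01 the simulated error is about 0.01% or less, because the type difference sits in the residual.

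**Step 4: candidate replacements, by simulation at ICC 0.01 (3 arms × 2 cities × 2 clinics × 100 men).**
- Clinic means adjusted for type, two arms (5 df), economic status without effect: 5.0% / 7.7% / 11.4% when none / half / all of the ICC is shared by city. This is valid only without a city effect.
- City means, variance pooled over three arms (3 df): 5.0% if economic status has no effect on the scale. If each arm holds one higher- and one lower-status city, the error falls to about 3% at a status gap of 0.1 SD, 0.4–1.0% at 0.2 SD and about 0.1% or less at 0.3 SD.
- The same, adjusted for status (2 df): 5.0%.

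**Step 5: precision at ICC 0.01.** SE = √(2 × DE/400); the 95% half-width is t × SE, in SD units.
- Plain t-test: 1.96 × √(2/400) = 0.139.
- Clinic level, 5 df: 2.571 × √(2 × 1.99/400) = 0.256.
- City level, 2 df: 4.303 × √(2 × 1.99/400) = 0.43 with no city share, and 4.303 × √(2 × 2.99/400) = 0.53 with all of it at city level.

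**The case against.** Table 2 gives a short method label, not a specification. It could mean a t-test on cluster means, which would respect clustering. Nothing in the documents says so, and on unadjusted clinic means the test would hardly ever reject when clinic types differ (Step 3). Either reading needs correcting.

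The balance on clinic type gives some protection, and that stands: a reader might infer that differences between MSM-led and public clinics inflate the error, but they make the test slightly conservative. Only correlation beyond the balanced factors does harm.

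No ICC is given, so the inflation cannot be stated as a fact. That also stands. The omission is certain; its size is not. But the level at which the test turns liberal is very low (Step 2), and a cluster trial should not depend on falling below it.

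Plain city means may seem the obvious remedy. They are not safe as they stand if economic status is balanced, because they are then conservative (Step 4).

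Finally, these are secondary outcomes, and Table 2 reports several others only descriptively. That limits the weight of the point and offers a simple way out.

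**Conclusion.** The point holds. For four secondary scales the plan names a test that, run on individual men, has no allowance for the clustered allocation, and it names no arm pairs. Under the Step 1 assumptions the true error of a nominal 5% test is about 6% to 42% for clinic ICCs of 0.001 to 0.05, and 26% to 55% for ICCs of 0.01 to 0.05 lying wholly at city level. With zero residual ICC there is no inflation.

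Three stronger readings are not supported. The primary result is not affected by this point: test uptake and the two main hypotheses have mixed models. The documents do not show that the scale analyses will be wrong by any particular amount, since they give no ICC. Nor does the point extend to every RE-AIM comparison: the t-tests and chi-square tests named in the implementation evaluation would share the problem only for measures on individuals, or repeated within clinics, that are not aggregated, and Table 3 lists mostly descriptive analyses.

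This should be corrected before analysis, but it does not threaten the trial's main conclusion.

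**What to change.** 1. State the unit actually allocated. The abstract keeps both clinics of a city together, whereas the sample size section names the clinic; reconcile the two. Also settle whether every city has both clinic types: Figure 2 says so and Site selection names six cities, but Study setting has "We will implement the study in Guangdong cities with either (or both) public STD and MSM-led clinics".
2. In Table 2, replace the t-test for the four scales with an analysis at that level, adjusted for the factors balanced at randomization (clinic type, and city economic status if it is used as the Design overview says), with small-sample degrees of freedom.
   - If clinics are allocated independently: a linear mixed model with a clinic random intercept, or clinic-level summaries.
   - If cities are allocated: city-level summaries, each the unweighted mean of its two clinic means so that clinic type cancels, adjusted for economic status where it was balanced. A city with only one clinic would need adjustment for type.
3. Name the arm pairs, for example the two in the RCT Data analysis section: community-engaged against standard, and standard against control.
4. If too few degrees of freedom remain (2 for status-adjusted city means over three arms), report estimates with intervals that respect the clusters, or report descriptively without p-values.

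The cost is wording and a different analysis of data already planned, with no design change. Intervals widen and power falls for these outcomes: at ICC 0.01 the half-width goes from 0.139 SD to about 0.26 SD at clinic level, or 0.43–0.53 SD at city level with 2 df.

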Pay-it-forward has a person receive a gonorrhea test as a gift from the local community and then decide to donate money to support subsequent testers (**Figure 1**)^{17,18}. Pay-it-forward fits within the broader field of behavioral economics, which uses multiple disciplines to understand human decision-making. Pay-it-forward chains of giving are sometimes driven by unconnected generous individuals¹⁸, but more often organized by a group with a common purpose^{19,20}. Studies have shown that pay-it-forward can be sustainable and promote generosity²¹.

[figure not shown]

Figure 1. Overview of pay-it-forward. *Participatory activities such as open calls to create handwritten messages in the community-engaged implementation strategy. A warm glow refers to a positive feeling after receiving a gift.

Our previous pay-it-forward research showed that it was associated with a substantial increase in gonorrhea test uptake compared to standard of care^{22,23}. However, these studies have several limitations. First, the projects were mostly, although not entirely, implemented at MSM-led clinics. These clinics serve MSM who are more likely to disclose their sexual orientation compared to MSM who present to public clinics. Alongside the MSM volunteers at MSM-led clinics, these sites are likely in a better position to organize MSM community engagement activities¹⁵. In addition to MSM-led clinics, public clinics also provide gonorrhea testing and treatment for MSM. Public clinics include HIV testing sites and STD clinics that receive support from public health authorities. Public clinics have higher rates of linkage to care and are more likely to have antibiotic therapy on-site. Second, MSM included in these two studies were mostly younger, better educated, higher income, and more willing to donate. The pay-it-forward intervention needs to be evaluated in additional cities and different types of clinics (i.e., both MSM-led and public clinics). Last, the previous study showed that pay-it-forward was effective compared to the standard of care, but explicit and intentional support for implementation is needed for scale-up. Lack of implementation evaluation limits our understanding of the implementation process, and community-engaged strategies are needed to maximize efficiency and effectiveness. These underscore the importance of implementation research to inform contextually appropriate strategies to implement pay-it-forward most effectively at scale.

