and qualitative data separately) and the results were interpreted together. Generalized mixed-effects models will be used to examine two main hypotheses: one comparing the superiority of the community-engaged strategy compared to the standard pay-it-forward strategy; and another comparing the superiority of the standard pay-it-forward strategy to the control arm. The estimated intervention effects will be reported with 95% C.I.s and p-values. Descriptive analysis will be used to summarize the characteristics and behaviors of the participants in each arm.

Implementation evaluation

The RE-AIM framework has been extensively used in implementation research to evaluate the implementation of evidence-based interventions. At this stage, we will evaluate the other dimensions of the implementation of the standard pay-it-forward and the community-engaged pay-it-forward arms with a view to understand both the factors that influence men to get tested and those that motivate men to donate. Given the novelty of pay-it-forward to raise funds, its sustainability partly depends on men willing to donate. Understanding the drivers of financial sustainability across individuals and clinics may help inform policymakers and interested researchers in resource-limited settings about the potential of using the strategy to promote underfunded public health services.

We will use a sequential explanatory mixed methods design.⁹³ In this design, quantitative data is followed up with qualitative methods to expand or explain the quantitative results. The quantitative component of our design will measure reach, implementation, adoption and maintenance by adapting validated implementation research instruments to assess acceptability and appropriateness at the individual level (related to adoption) and fidelity and organizational readiness at the clinic level (related to implementation). Details of these instruments are provided in Table 3 below. The qualitative data will use in-depth interviews grounded in upstream and social reciprocity theories to explore the processes and mechanisms that affect the results, and how these differ by individual (geography and socioeconomic) and organizational (geography and readiness) characteristics. Our mixed methods study will be conducted during and after the RCT.

Quantitative surveys

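### Table 2 examines age only as 30 or under v over 30; if the effect changes steadily with age, testing moderation on that split would lose a material share of the information

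*Combined protocol and SAP*

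**What the plan says.** In Table 2, under the subgroup analyses, one row reads "Gonorrhea and chlamydia testing uptake by age group". Its source is given as "Self-reported socio-demographic data from baseline survey" and its analysis as "≤30years vs. >30years". The row names no model and no test, and gives no reason for choosing 30.

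The Data analysis section of the cluster RCT does not mention age. There, "Generalized mixed-effects models will be used to examine two main hypotheses": community-engaged against standard pay-it-forward, and standard pay-it-forward against control. No arm-by-age term is described.

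On moderation, the abstract's Discussion says: "This study will answer compelling scientific questions about how best to implement pay-it-forward and the individual and organizational characteristics that moderate it". The list of contributions repeats this, and the second objective also refers to moderation by individual and organizational characteristics.

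On who is enrolled: "The inclusion criteria at public clinics include men who are at least 18 years old". The MSM-led clinics have the same lower limit, and no upper limit is stated. The Background says of the earlier pay-it-forward trials that "MSM included in these two studies were mostly younger, better educated, higher income, and more willing to donate".

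**The concern.** A split at 30 treats men of 18 and 30 as alike and men of 30 and 31 as different, and it pools everyone over 30 into one group. If the benefit of pay-it-forward rises or falls gradually with age, the split blurs that gradient, makes it easier to miss, and makes the answer depend on where the cut falls.

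Age is worth examining here. The earlier studies enrolled mostly younger men, and this trial takes men from 18 with no stated upper limit, so whether the effect carries over to older men is a natural question. Age also varies between men within a clinic, whereas clinic type is fixed for each of the 12 clusters.

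This is a different matter from whether any arm-by-subgroup interaction is tested. A correctly specified interaction test on the two groups would still carry the loss worked out below.

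**Working it through.** **Inputs from the documents.** 12 clusters, 4 per arm, 100 men per cluster, 1200 men in all; two pairwise hypotheses; a cut at 30; minimum age 18. Each arm has 4 × 100 = 400 men, so each pairwise contrast has about 800.

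**Inputs not in the documents (assumed, with ranges).** The age distribution, the share of men aged 30 or under, and the shape of any change in effect with age.

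**The plan's own figure.** The plan states no power for the age analysis. Its only related figure is for the main comparison: "In order to achieve a 90% power and allow for 0.05 type-I error", 12 clusters are needed. That cannot be reproduced or refuted, because uptake rates and the intracluster correlation are not given. As an illustration, 20% v 40% uptake with an effective size of 400/(1 + 99 × ICC) per arm gives 99%, 95% and 72% power at an ICC of 0.01, 0.02 and 0.05 (normal approximation). Nothing below depends on it.

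**Step 1: formula.** If the treatment effect is linear in age, the share of interaction information kept by a two-group split is the squared correlation between age and the group indicator. For normally distributed age with a share p on one side of the cut, this is φ(z_p)² / [p(1 − p)], where φ is the standard normal density and z_p the p-quantile.

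**Step 2: normal age.**

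| Split at 30 | Share kept | Loss | Loss × 800 men |
|---|---|---|---|
| 50/50 | 0.1592/0.25 = 0.637 | 36.3% | 291 |
| 60/40 | 0.1493/0.24 = 0.622 | 37.8% | 302 |
| 70/30 | 0.1209/0.21 = 0.576 | 42.4% | 339 |

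Put the other way, the split needs 1/0.637 = 1.57 to 1/0.576 = 1.74 times as many men for the same precision on the gradient.

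**Step 3: other age shapes.** The squared correlation was computed directly for assumed distributions starting at 18, still with a linear gradient.

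| Assumed age distribution | Aged 30 or under | Loss |
|---|---|---|
| Uniform, 18-42 | 52% | 25% |
| Normal (mean 30, SD 8), cut off below 18 | 52% | 34% |
| Right-skewed, mean 32, SD 9 | 54% | 41% |
| Right-skewed, mean 38, SD 12 | 32% | 56% |

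The first and last rows are the extremes of the shapes tried.

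**Step 4: check on the logistic scale.** Trials of 800 men in two arms were simulated with a log-odds interaction of 0.35 per SD of age and no clustering.

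| Age distribution | Loss | Power, age in years | Power, split |
|---|---|---|---|
| Normal, 50/50 at 30 | 37% | 63% | 44% |
| Normal, 30/70 at 30 | 44% | 65% | 44% |
| Right-skewed, mean 32, SD 10 | 43% | 62% | 40% |

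The losses agree with the formula. The power values depend on the chosen interaction size and serve only to compare the two codings; they do not forecast this trial's power.

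**Step 5: the limiting case.** If the effect is constant up to 30, changes there, and is constant afterwards, the two-group indicator is the correct covariate and the loss is nil.

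**The case against.** The strongest reply is that the loss concerns a test the plan does not describe. The age row gives a contrast and no model, so it may be meant only as a display. A two-group display fixed in advance is conventional and easy to read, and because the cut was set beforehand there is no ground to suspect that it was chosen from the data. The missing interaction term is arguably the larger gap. All of this stands and limits the point. It does not remove it: moderation by individual characteristics is a stated aim, the split is the only age analysis listed, and adding an interaction on the split would leave the loss in place.

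Three stronger readings are tempting, and the documents do not support them.

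- **That 36-42% is a property of this trial.** It needs roughly normal age, 30-70% of men on each side of 30, and a linear gradient. The documents give no mean, SD or share aged 30 or under, so the figure is an example within a wider range.
- **That the loss amounts to some 430-510 of the 1200 men.** That multiplies the loss by all three arms. Table 2's primary-outcome row does speak broadly of control against pay-it-forward, but the Data analysis section sets out two pairwise hypotheses, so about 800 men is the fitting base.
- **That age is the key moderator, so that a main question of the trial is compromised.** The moderation statements do not name age. The Implementation evaluation section, describing how interviews will explore differences, names geography and socioeconomic position as the individual characteristics.

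The continuous analysis also brings a linearity assumption of its own, which is why a spline check belongs with it.

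**Conclusion.** The point holds as a modest improvement to a subgroup analysis. Age is examined only as two groups, the cut is unexplained, and nothing else in the documents keeps age continuous. If the effect changes steadily with age, testing moderation on the split would lose roughly a quarter to a little over a half of the information across the age shapes tried, with the normal-age example lying between. That conclusion rests on an assumed age distribution and a linear gradient, and the calculations ignore clustering. The primary outcome, the sample size and the two main arm comparisons are not affected.

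**What to change.** Amend the age row of Table 2 to say that moderation by age is tested with an arm-by-age interaction in the generalized mixed-effects model already planned for the primary outcome. Enter age in years as a linear term, include its main effect, and refit with a 3-knot spline to check linearity. Keep the 30-or-under and over-30 groups for display only.

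The cost is about one line of text and no extra participants. If age is recorded in years, no new data are needed; the documents say only that it comes from the baseline survey, so the sponsor should confirm that it is not collected in bands. The downsides are a linearity assumption to check and one more result, a curve of effect by age, to present beside the two groups.

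If the sponsor has a substantive reason to expect a change in effect at 30, stating it in the same row would justify the split.
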